This unprecedented prevalence of hypertension is influenced by the growing elderly population due to increased life expectancy. In addition, habitual risk factors, such as increased caloric and salt intake combined with a sedentary life-style, have facilitated=fostered the age-related surge in blood pressures. That being said, very few interventions have been successful in achieving extended and long-lasting control with any of these risk factors. For decades, studies have extensively searched for more effective interventions, but anti-hypertensive pharmacotherapy remains the most important means (I would rather say tool) for reducing high blood pressures. However, anti-hypertensive pharmaceuticals, even though being fairly effective and accessible at an affordable price, are far from ideal. Indeed, although a great majority (87.5%) of those diagnosed with hypertension receive regular pharmacological therapies, only a minority (32.5%) show controlled blood pressures (SBP < 140 mmHg), despite the fact that nearly one third of them already receive 2 or more drugs⁸. Using Austria as an example, controlled blood pressure is achieved in only 17% of hypertensive patients⁹ and data from other European countries reveals

comparable results. **Therefore, further investigation is necessary to develop better therapies for managing hypertension and avoiding hypertension-related complications.**

In this regard, spermidine — a natural caloric restriction mimetic — delays the onset of hypertension in a strain of rats sensitive to salt intake². Our initial goal of preventing these animals from developing fatal heart failure induced by severe hypertension led us to discover a direct effect of spermidine on hypertension². This finding was further corroborated by an epidemiological study in humans (BRUNECK study), where we observed that higher dietary intake of spermidine correlated with reduced blood pressure and decreased cardiovascular events². Interestingly, spermidine supplementation in elderly subjects coincided with a trend towards reduced blood pressure (a phase I safety trial)¹⁰. Even in the absence of hypertension, preclinical evidence supports vascular benefits of spermidine treatment, which was shown to reduce age-related vascular stiffness and endothelial dysfunction¹¹.

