2.1 Trial design

The study is designed as a single-centre, placebo-controlled, double-blind and randomized controlled trial with a balanced 2x2 crossover design and a washout period between treatment arms. Specifically, half of the recruited patients will be treated with spermidine for eight weeks, followed by placebo for eight weeks. The other half of patients will first receive placebo and then spermidine. There will be a washout period of four weeks between the first period of eight weeks and second period of eight weeks to separate the two interventions in both arms, which will avert any carryover or residual effects. A balanced 2x2 crossover trial design is ideal for this study for the following two reasons:

(i) Physiological reason: spermidine levels in the body are substantially affected by the diet. Thus, patients with different dietary habits could already have different spermidine levels at baseline (i.e. before starting the trial). Even if patients were randomized into 2 groups correcting for baseline measured circulating spermidine, this wouldn't guarantee that spermidine levels in the body tissues are comparable without confirming via biopsy, not to mention that food intake would need to be strictly controlled and be identical in both arms throughout the trial. For this reason, crossover/repeated measurements are not only more practical, but rather essential for our proposed study. The effect of any other confounding factors (e.g. body mass index, age, smoking, baseline blood pressure, LDL, etc.) will be also reduced to a minimum as every patient will serve as his/her own control.

(ii) Statistical reason: a crossover design is particularly efficient as it provides the highest power-to-sample size ratio. Thus, the study endpoints can be examined with as few patients as possible.

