2.3 Trial population

The trial population consists of mixed adults from both genders screened during hospitalisation at a medical clinic. Patients selected must present with elevated blood pressure despite being treated with at least two guideline-recommended drugs. This approach secures a trial population with well-established arterial hypertension and ensures that patients will have received baseline treatment based on the guideline recommendations before being enrolled in the proposed study. Therefore,

our study offers an additional novel and innovative strategy for patients following their initial baseline treatment which failed to fully manage their hypertension. Patients who need to be excluded due to systolic blood pressures > 180mmHg will directly be advised to get further treatment at the outpatients clinic and the educational program herz.leben.

Recruitment

Patients with systolic arterial hypertension of more than 150 mmHg during hospitalisation despite being treated with at least two guideline-recommended drugs will be informed of the possibility to participate in the trial. If they consent, patients will be contacted four weeks later by telephone to check for unchanged medication and blood pressure. Patients with persistent arterial hypertension (>150 mmHg), despite being on a consistent medication routine with at least two guideline-recommended anti-hypertensive drugs within the last four weeks, will be invited for a screening (Visit 1) at our hospital. Upon confirmation of sustained high blood pressure (>150 ≤180mmHg) and fulfilment of inclusion and exclusion criteria, patients will again be informed that participation in the trial is voluntary before signing the informed consent form. After signing the ICF, patients will be randomized in a 1:1 ratio and a block size of 46 using the web-based randomizer (<https://randomizer.at/>) provided by [name] (Institute for Medical Informatics, Statistics and Documentation – IMI, Medical University of Graz). We aim to have both genders equally represented within the trial population. We will perform a gender-specific analysis of clinical and biochemical assessments.

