3.5 QoL assessment

The standardized and well-established SF-36 questionnaire will be used to evaluate a subjective quality of life of the patients.

4 Safety and risk management

The planned daily dose of spermidine is an approved dietary supplement extracted from spermidine-rich wheat germ (see <http://eur-lex.europa.eu/legal-content/EN/TXT/PDF/?uri=CELEX:32017R2470&from=EN>). Additionally, spermidine is part of a standard healthy diet, present in a wide variety of foods. Therefore, the dose of 4 mg spermidine per day is unlikely to cause any harm to the patients participating in the study. The reduction in blood pressure would be a beneficial therapeutic effect considering the hypertensive baseline. However, a NO/arginine-mediated blood pressure-lowering effect may also cause headaches, dizziness or tachycardia. The study protocol does not interfere with standard baseline therapy. Upon study completion, patients will be invited to participate in the educational program “herz.leben” (ADD link to the webpage!) and, therefore also receive optimal lifestyle modification training.

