4.3 Potential risks within the study design

All clinical assessments in this trial are standard methods and well established within the Department of Cardiology (MedUniGraz) and its clinical trial section. Thus, the applicant does not expect any methodological risk with respect to the trial. The recruitment of patients into this clinical trial will be based on the cooperation between the applicant and the herz.leben project, in which 120 highly motivated patients per year have been prospectively enrolled since 2007. Therefore, we do not anticipate having problems with recruiting 42 patients from this educational program within 12 months and expect these patients to fully adhere to the study protocol.

Saliva collection by swabbing is a very convenient and non-invasive method for collecting cells in clinical practice. However, saliva samples might not contain enough cells to perform all analyses, including the assessment of autophagic activities. Therefore, whole blood and blood cells (e.g. PBMCs) will be used to detect differences in autophagy, immune cell, and polyamine metabolite profiles. We work under the hypothesis that spermidine induces autophagy in hypertensive patients. If we fail to detect increased autophagy markers upon spermidine supplement, we will use

our data on plasma metabolites (such as L-arginine) and any detected changes in circulatory cell profiles to propose an alternative mode of action (potentially autophagy-independent). If spermidine levels are not increased in whole blood or plasma, our efforts will concentrate on the detection of spermidine-induced changes in polyamine metabolism by analyzing metabolites (i.e. precursors and derivatives of spermidine) in human plasma samples. Moreover, saliva samples offer an additional “tissue”-like sample that will prove the bioavailability of spermidine originating from the administered supplements.

5 Statistical considerations and data analysis

Obtaining repeated measurements from the same patients in response to both treatments has fundamental physiological reasoning (see 3.1) and necessitates completing the study protocol. For this reason and because the trial is designed to measure the treatment efficacy, rather than adherence, patients who drop out before completing the protocol (4 visits) or their baseline treatment regimen changes due to medical reasons will be excluded to maintain a balanced crossover analysis of this trial.

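### Does recruiting from the herz.leben lifestyle programme leave it open whether training runs during the crossover, and does that threaten the treatment comparison?

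*Combined protocol and SAP*

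**What the plan says.** herz.leben appears in three places.

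- **Section 4.3** (feasibility) bases recruitment on cooperation with the programme, which has enrolled 120 patients a year since 2007, and states "we do not anticipate having problems with recruiting 42 patients from this educational program within 12 months".
- **Section 4** (safety) says "Upon study completion, patients will be invited to participate in the educational program" and that they "therefore also receive optimal lifestyle modification training".
- **Section 2.3** says of patients excluded for systolic pressure above 180 mmHg that they "will directly be advised to get further treatment at the outpatients clinic and the educational program herz.leben". For the trial itself, "The trial population consists of mixed adults from both genders screened during hospitalisation at a medical clinic".

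Section 2.1 defends the crossover on the ground that "spermidine levels in the body are substantially affected by the diet", and says other confounders are minimised "as every patient will serve as his/her own control". Section 1.1 lists "habitual risk factors, such as increased caloric and salt intake combined with a sedentary life-style" among the causes of rising blood pressure.

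Section 2.4 requires stable drug treatment and does not mention lifestyle programmes. Section 5 analyses change from baseline in a mixed model with Treatment, Period and Sequence fixed and Subject random. It removes patients whose baseline treatment regimen changes for medical reasons.

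Section 2.6 enrols 46 patients. Section 2.8 gives 18 months of recruitment within a 21-month project.

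**The concern.** Patients recruited from a programme already have some link with it, so inviting them to it afterwards is odd. Read together, Sections 2.3, 4 and 4.3 do not state whether a participant has the training before, during or after the trial.

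On the protocol's own reasoning this could matter. Being one's own control protects against factors that stay put for 20 weeks. Training that changes salt, calories and activity aims at factors that the protocol links to blood pressure, and a changed diet could also shift background spermidine intake. If it began part-way through, the two periods would differ in more than the study product. Table 1 does not list attendance, and Section 5 does not name the programme when it defines a changed regimen. An analyst might therefore have to decide afterwards whether an attender stays in the analysis.

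The same sentence in Section 4.3 also disagrees with the plan on the number of patients and the recruitment time.

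**Working it through.** **1. The plan's own sample size.** Inputs from Section 2.6: effect 5 mmHg, SD 13 mmHg, r = 0.65, two-sided 5%, power 80%.

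- Variance of the within-patient difference = 2 × 13² × (1 − 0.65) = 118.3, so SD = 10.88.
- n = (1.96 + 0.8416)² × 118.3 / 25 = 37.1, rounded up to **38**, as stated.
- 38 / 0.85 = 44.7, so 45, or **46** for two equal sequences, as stated.
- Power at 38 is 80.9% (normal) or 78.7% (noncentral t, 36 df).

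**2. Training effect common to all patients.** Suppose training shifts everyone by the same amount in one period. With 19 patients per sequence the shift cancels from the treatment contrast. With unequal completers the Period term removes it. If that term were left out, a 5 mmHg shift with 21 and 17 completers would bias the contrast by 5 × (21 − 17)/38 = 0.53 mmHg in absolute value. The plan includes the term, so this bias does not arise.

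**3. Training effect that varies between patients.** Let s be the between-patient SD of a response that enters one period's change score only. The documents give no value for s, so these are assumptions. The variance becomes 118.3 + s².

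| s (mmHg) | Variance | SD | Power at 38, t (normal) | Completers for 80% (normal) |
|---|---|---|---|---|
| 0 | 118.3 | 10.88 | 78.7% (80.9%) | 38 |
| 3 | 127.3 | 11.28 | 75.8% (78.0%) | 40 |
| 5 | 143.3 | 11.97 | 70.7% (73.1%) | 45 |
| 8 | 182.3 | 13.50 | 60.3% (62.7%) | 58 |

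The expected treatment contrast is unchanged throughout, because sequence is randomised and blinded. Only precision suffers.

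**4. When does that variance arise?** Let a lasting response g be gained at one point, and compare the two change scores. The variance added to their difference is:

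| Response gained | Each period's own baseline (Visits 2 and 4) | Single baseline (Visit 2) |
|---|---|---|
| Before Visit 2 | 0 | 0 |
| During period 1 | s² | 0 |
| During washout | 0 | s² |
| During period 2 | s² | s² |
| Equal gain g in each period | 0 | s² |
| After Visit 5 | 0 | 0 |

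For example, with period-specific baselines a gain in the washout is in both Visit 4 and Visit 5 and drops out of the second change score. Section 5 does not say which baseline is meant. Under either reading several timings cost nothing, including both that the text suggests: past attendance with a settled effect, and attendance after completion.

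**5. The clerical figures.**

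- Patients: 46 is the derived number, and the block size of 46 in Section 2.3 agrees with it. It leaves 46 × 0.85 = 39.1 completers. The 42 in Section 4.3 would leave 42 × 0.85 = 35.7, but no calculation uses it.
- Time: 20 weeks is 4.6 months, and 18 + 4.6 = 22.6 months, more than the 21-month project. The calendar dates in Section 2.8 (February 2020 to June 2021) span 15.0 to 16.9 months, or 19.6 to 21.5 months with follow-up. No analysis depends on this.

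**The case for a change.** The strongest case for a change is that the textual conflict does not depend on any assumption, and that repair is cheap: a few words, an attendance item on the case report form and a sensitivity analysis. At 120 programme patients a year, attendance close to the trial is plausible. Whether an attender's regimen has changed would be better settled before the data are seen.

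The conflict stands: the recruitment source in Section 4.3 does not match Section 2.3, and reconciling the passages would be good housekeeping. The rest is weaker.

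- Section 4.3 argues feasibility and sets no training schedule. The referral in Section 2.3 concerns excluded patients, so it says nothing about participants.
- The exclusion in Section 5 is limited to regimen changes made for medical reasons. Section 2.3 uses baseline treatment for guideline-recommended drugs. Attending an educational course does not naturally fall under that wording.
- Table 1 is not exhaustive. It omits the six-minute walk test that Section 3.1 requires at every visit, so the absence of attendance there shows little, and the case report form is not among the documents.
- A sensitivity analysis without attenders would select on an event after randomisation and could only be supportive.

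A further argument is that a 2×2 design cannot separate treatment-by-period interaction from Sequence and carryover. That is true, but it applies to any 2×2 crossover with or without herz.leben. Treatment, Period and Sequence already saturate the four cell means, so rewording Section 5 would alter no estimate.

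**Conclusion.** No change to the plan is needed. The documents are inconsistent about where patients come from, and Section 4.3 carries a patient number and a recruitment time that differ from those in Sections 2.6 and 2.8. These are slips in a feasibility paragraph; the operative enrolment is 46.

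The statistical harm is inferred. It requires training to begin or run during the 20 weeks, which no passage says. It also requires responses that differ between patients and fall unevenly across the change scores. Even then the treatment contrast stays unbiased and only power is lost: about 3 points at s = 3, 8 at s = 5 and 18 at s = 8 (t-based, 38 completers). Those SDs are illustrative.

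This conclusion rests on the Period term being fitted as planned and on sequence staying randomised and blinded. Within that, the plan as written gives a sound comparison, and an analyst would sensibly read the regimen-change exclusion as referring to drug treatment.

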2.8 Project duration and milestones

We envision that a period of 21 months will be needed to successfully accomplish this study. The recruitment (18 months) is planned as follows:

First patient visit:	February 2020
Last patient enrolled:	June 2021

3 Methods

3.1 24h BPM

During each of the four visits patients will be supplied with an ambulatory blood pressure measurement (ABPM) device (Mobil-O-Graph® PWA, I.E.M. GmbH, Stolberg, Germany). After 24 hours of continuous BPM at their homes, patients will remove the device and return it to the study center via postal service. Mobil-O-Graph® PWA is a well established device to measure central blood pressure and pulse wave velocity used and validated in multiple clinical trials and settings. Despite being a non-invasive technique good accuracy compared to intra-aortic readings has been proven (linear correlation $R=0.81$, $p < 0.0001$) in 120 patients (see validation data on www.iem.de/en/health-management/studies-validations.html and a bibliography at www.iem.de/files/content/DE/IEMintern/Support/Hintergründe/Bibliography%20Mobil-O-Graph%20Blood%20Pressure%20PWA%202.9.pdf) During the visit on-site blood pressure measurements and a standardized 6MWT will be conducted at every visit.

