4.2 Study discontinuation

One or more of the following incidences would lead to a discontinuation of the study for a single patient (drop-out):

- Withdrawal of consent
- Intolerable investigational drug-related effects
- Severe violation of the study protocol
- New onset of an exclusion criterion during the treatment period
- Decrease in blood pressure of more than 40 mmHg with symptomatic hypotension

Early discontinuation of the study will be taken into a consideration if the risk-benefit relationship worsens:

- Intolerable investigational drug-related effects in more than 10 patients
- Decrease in blood pressure of more than 40 mmHg with symptomatic hypotension in more than 10 patients

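### The only analysis set removes every non-completer and every medically driven regimen change, discarding usable period 1 data; the expected bias is small, and the rule is cheap to replace

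*Combined protocol and SAP*

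**What the plan says.** Section 5 states that "patients who drop out before completing the protocol (4 visits) or their baseline treatment regimen changes due to medical reasons will be excluded". It gives two reasons. The first is that measuring each patient under both treatments has a physiological basis, so the protocol must be completed. Section 2.1(i) supplies the argument: tissue spermidine varies with diet, so patients should act as their own controls. The second is "because the trial is designed to measure the treatment efficacy, rather than adherence". The stated aim is a balanced crossover analysis. The analysis is a mixed linear model on change from baseline, with subject random and treatment, period and sequence fixed. Neither section 5 nor any other section gives an all-randomised set, a missing-data method or a sensitivity analysis.

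Other relevant provisions:

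- **Design (2.1):** "single-centre, placebo-controlled, double-blind and randomized controlled trial with a balanced 2x2 crossover design".
- **Population (2.3):** "Patients selected must present with elevated blood pressure despite being treated with at least two guideline-recommended drugs".
- **Schedule (2.2, Table 1):** 24h blood pressure at weeks 0, 8, 12 and 20.
- **Visits (3.1):** "During the visit on-site blood pressure measurements and a standardized 6MWT will be conducted at every visit".
- **Safety (4):** a "blood pressure-lowering effect may also cause headaches, dizziness or tachycardia".
- **Drop-out reasons (4.2):** these include "Intolerable investigational drug-related effects" and a symptomatic hypotensive fall exceeding 40 mmHg.
- **Sample size (2.6):** 38 patients needed, 46 enrolled, 15% drop-out expected.

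**The concern.** Membership of the only analysis set is decided after randomisation, by events that treatment or outcome can influence. Section 4.2 makes drug intolerance and an extreme fall in blood pressure reasons to leave. Patients enter uncontrolled on at least two drugs and have on-site readings at each visit, so a medically driven regimen change can follow blood pressure. Completers may then differ from the randomised patients, and differently in the two sequences.

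The rule also discards data that are valid for the sponsor's own question. A patient who leaves or changes regimen after week 8 has already given a full period 1 change score on unchanged therapy.

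At stake are a possible shift in the estimate and the reader's ability to see whether the exclusions mattered. With only a completer set, neither could be checked.

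**Working it through.** **1. The plan's own figure.** Inputs from section 2.6: effect 5 mmHg, SD 13, r 0.65, two-sided 5%, power 80%.

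- SD of the within-patient difference = 13 × √(2 × (1 − 0.65)) = 10.88.
- n = ((1.960 + 0.842) × 10.88 / 5)² = 37.14, rounded up to 38. This reproduces the plan.
- 38 / 0.85 = 44.7, so 45, or 46 when made even for 1:1 allocation.
- At 15% loss, 46 × 0.85 = 39.1: about 39 completers and 7 excluded.

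**2. Does anything in section 5 require deleting period 1?**

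- *Both treatments in the same patient.* The within-patient contrast still comes from the complete pairs. A period-1-only patient adds between-patient information, which randomisation makes valid even if diet and tissue spermidine vary.
- *Efficacy rather than adherence.* Efficacy under unchanged therapy is kept by using only readings taken before drop-out or regimen change.
- *Balance.* Deletion makes each analysed patient complete but does not keep the sequences equal. In step 3, losses are 3.8–22.9% in spermidine-first and 5.5–29.1% in placebo-first. The mixed model does not need balance.

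**3. Bias under a common, treatment-blind trigger.** From the plan: SD 13, r 0.65, effect -5, entry range 150–180 mmHg, visits at weeks 0, 8, 12 and 20. Assumed: exchangeable correlation, mean SBP 155–165, and exclusion when SBP reaches 175 or 180 at week 8 or 12. The figure of 180 is also the plan's entry limit (2.3, 2.4), but its use as an on-study trigger is an assumption. Simulation used 3 million patients per setting before the entry cut; Monte Carlo error is about 0.01. Change is from each period's own baseline.

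| Mean / trigger | Deleted | Completers, raw | Completers, change | All available, raw | All available, change |
|---|---|---|---|---|---|
| 155 / 180 | 4.6% | -4.90 | -4.88 | -5.01 | -5.02 |
| 160 / 180 | 8.0% | -4.83 | -4.82 | -5.00 | -5.02 |
| 165 / 175 | 26.0% | -4.65 | -4.63 | -5.04 | -5.09 |

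With 39 pairs split 20:19, the SE on raw values is 0.5 × √(10.88²/20 + 10.88²/19) = 1.74. The largest raw bias is 0.35 / 1.74 = 0.20 SE. With a true effect of 0, completers are within 0.02 of 0. If the trigger is a noisier on-site reading (extra SD 10, assumed), 13.1–37.8% are deleted, completers give -4.87 to -4.74 (raw) or -4.82 to -4.70 (change), and the null result is within 0.03 of 0.

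**4. Exclusions in one treatment only** (mean 160, trigger 180 or 175 at week 8, true effect 0). Completers shift by 0.30–0.62 mmHg (raw) or 0.42–0.88 (change): upwards if only placebo patients are excluded, downwards if only spermidine patients are. Type I error becomes 5.3–6.4%. The available-data model stays within 0.13 of 0.

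**5. Intolerance on spermidine.** Assume individual effects with mean -5 and SD 5, and that the 5% or 10% with the largest falls leave. Completers give -4.47 or -4.02, and the available-data model gives the same. If intolerance is unrelated to blood pressure, the result is -4.99.

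**6. The rule on falls exceeding 40 mmHg.** With mean change -5 and SD 10.88, (−40 + 5) / 10.88 = −3.2 SD. About 0.06–0.08% of patients would meet it, or about 0.03 of 46, before symptoms are required.

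**7. Precision.** Adding period 1 of 7 patients to 39 pairs moves the raw SE from 1.742 to 1.718. Power (t, 37 df) goes from 79.8% to 80.9%, or to 81.3% with a shared week-0 baseline. The gain is about 3 points if each period has its own baseline.

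**The case against.** The strongest case for the sponsor is that the restriction matches the question. The trial is a within-patient efficacy comparison on stable medication, which is an inclusion criterion, and N already allows for 15% loss. Blinding makes a common trigger the likely case, and then the bias is at most 0.20 SE and towards the null. The explicit 40 mmHg rule removes almost nobody.

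Nor is the alternative uniformly better. It leaves selective intolerance unrepaired. With own-period baselines it errs slightly away from the null (up to -5.09). If loss depends on unrecorded period 2 pressure, it is worse than completers: raw -4.73 and -4.37 against -4.83 and -4.61 (means 160 and 165, triggers 180 and 175).

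All of this stands, and it limits the point to a minor one. It does not justify deleting period 1 or reporting only completers.

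Three stronger readings are tempting but not supported:

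- **Background drugs may be changed at will.** "The study protocol does not interfere with standard baseline therapy" is a safety statement in section 4. It shows only that a regimen change is possible.
- **180 mmHg is a stated withdrawal trigger.** Section 4.2 lists a newly arising exclusion criterion as a drop-out reason, but the 180 mmHg criterion is tied to the day of randomisation. Whether it applies later is unclear.
- **The estimate could be off by more than 1 mmHg.** Putting all of about 7 exclusions in one sequence, sorted on the week 8 outcome, gives -3.9 or -6.1 against a true -5. No figure in the documents supports so extreme a pattern.

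**Conclusion.** The point holds as a cheap improvement of minor severity. The rule is explicit and stands alone, it selects patients after randomisation on events that can follow outcome or drug effect, and it discards valid period 1 data without need.

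The likely bias is 0.1–0.4 mmHg towards the null, and about zero under no effect. Treatment-related exclusions, less likely under blinding, could give 0.3–0.9 mmHg in either direction under the null. These sizes rest on assumed means, triggers and exclusion patterns; only the SD, correlation, effect, entry range and visit weeks come from the plan.

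A reader might infer that the rule manufactures a false benefit or invalidates the trial. The documents do not support that: under blinding with a common trigger there is no shift under the null, and even one-sided exclusions take type I error only to 5.3–6.4%.

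**What to change.** Replace the exclusion sentence in section 5 with the following.

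1. **Primary analysis.** The planned mixed model, fitted by REML, on all randomised patients with a baseline and at least one end-of-period 24h SBP. Use every change score whose end-of-period reading precedes drop-out or regimen change; treat later scores as missing.
2. **Sensitivity analyses.** (a) The sponsor's completer, unchanged-regimen set. (b) All observed readings, including those after a regimen change. (c) A missing-not-at-random shift: impute under missing-at-random, add 5 and then 10 mmHg to imputed spermidine values only, then to imputed placebo values only, and report the shift at which the conclusion changes. The two step sizes are a choice. With 15% period 2 loss, a spermidine-only shift d moves the estimate by 0.5 × 0.15 × d, i.e. 0.38 mmHg at 5 and 0.75 at 10.
3. **Reporting.** Tabulate losses and regimen changes by treatment, period, sequence and reason, including patients lost before week 8.

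The cost is revised text and a little more analysis work; visits, model and N are unchanged. The primary analysis would rest on missing-at-random and would not repair selective intolerance, which is why the shift analysis and the loss table are needed.
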